6.10 Data collection

After cannulation, the authorised ECMO fellow/trial coordinator will collect data on pre-printed forms to characterise the patients who are approached about the trial (e.g. eligibility criteria, key demographic data, willingness to participate and, if not willing, main reason for refusal). These data will be entered promptly in the master subject tracker in order for the trial registration number to be generated for a study participant.

Other pre-ECMO data likely to influence the speed of post cannulation recovery, procedure details (cannulation, details of the ECMO circuit), morbidity, duration of ICU and hospital stay and other non-biochemical secondary outcomes will also be collected prospectively on pre-printed forms, including dates and times of relevant outcomes.

These data will be entered into a database immediately after the end of follow-up. In the event that a patient has been withdrawn from the study, we will continue to analyse any data already collected, unless the patients expresses a wish for their samples and any associated data to be destroyed.

Source data will be collected prospectively on designated CRF's. In addition, the patient's medical notes will be a source for additional clinical data, including blood and urine results performed in the clinical setting. University laboratory databases will be the source for other trial specific biochemical markers analysed in the blood and urine.

Protocol adherence will be evaluated through the monitoring of protocol violations defined as any change, deviation, or departure from the study design or procedures of research project that is not approved by the Sponsor and Ethics Committee prior to its initiation or implementation.

Protocol violations will be categorized as major or minor violations, according to the following definitions:

A major protocol violation:

- a serious and/or continuous failure on the part of the study team to comply with the protocol, standard operating procedures, good clinical practice (GCP), trial regulations.
- has significant negative impact to subject safety. It may or may not result in actual harm to the subjects.
- Significantly damages the completeness, accuracy and reliability of the data collected for the study.

A minor protocol violation/deviation/non-compliance:

- Does NOT represent a serious or continuous failure on the part of the study team to comply with the protocol, standard operating procedures, GCP, trial regulations.
- Does NOT significantly impact subject safety or substantially alter potential risks to subjects
- Does NOT result in actual harm
- Does NOT significantly damage the completeness, accuracy and reliability of the data collected for the study

Clinical protocol non-adherence will be defined as the failure to obtain the specified clinical data, blood volume or urine samples required for analysis at the required time. Protocol violation concerning the time of sample collection will be defined as a deviation of more than 6 hours from the planned collection time for the baseline data, and 12 hours for the remaining time points. Laboratory protocol non-adherence will be defined as the failure to complete laboratory essay as described in the protocol.

6.11 Patient recruitment and consent

Patients who meet the inclusion criteria and have been referred for ECMO at the Glenfield Hospital will be considered eligible for the study. Parents/guardians will be required to provide full written informed consent. Patient's willingness to participate cannot be assessed since all the participants are younger than 1 month, therefore, they will be considered as unable to provide consent or assent. According to the Children Act and the Children Act (Northern Ireland) Order, parents and those with parental responsibility are allowed to consent to medical treatment or research on their behalf. Consent of only one parent is required. Patients' parents/guardians are expected to read and understand the parent/guardian information leaflet and (with the assistance of a member of the clinical team) understand the purposes and consequences of the study to the patient at a level suitable for them.

Patients can be formally enrolled only if emergency consent (59, 60) is obtained within 12h from ECMO cannulation. Details of all patients approached for the trial and reason(s) for non-participation (e.g. reason for being ineligible or patient refusal) will be documented.

Since the Glenfield Hospital is a national paediatric referral centre collecting patients from different parts of UK, we expect that a percentage of parents/guardians will not reach the Hospital within the first hours from cannulation and will not be promptly available onsite. Moreover, we expect that in rare cases the mother will not reach the hospital for days after ECMO start due to delivery's complications or health reasons. On the other hand, it is important to establish baseline values in order to test our hypothesis. For that reason, the first sample has to be collected within 12 hours from the cannulation. The Regulations prescribe a hierarchy for determining who should be approached to give informed consent on behalf of a minor prior to their inclusion in the trial as shown in Table 4. The provisions for informed consent by a legal representative only apply if due to the emergency nature of the trial, no person with parental responsibility can be contacted prior to the proposed inclusion of the minor.

For the reasons discussed above, the recruitment strategy will follow the scheme described in the following flowchart.

[figure not shown]

Table 4		
Person who may give the consent	Definition	Commentary
Parent	A parent or person with parental responsibility	Should always be approached if available
Personal legal representative	A person not connected with the conduct of the trial who is: (a) suitable to act as the legal representative by virtue of their relationship with the minor, and (b) available and willing to do so	May be approached if no person with parental responsibility can be contacted prior to the proposed inclusion of the minor, by reason of the emergency nature of the trial
Professional legal representative	A person not connected with the conduct of the trial who is: (a) the doctor primarily responsible for the medical treatment of the minor, or (b) a person nominated by the relevant health care provider (e.g. an acute NHS Trust or Health Board).	May be approached if no person suitable to act as a personal legal representative is available. Informed consent must be given before the minor is entered into the trial

6.11.1 *Parents/guardians with parental responsibility available within 12 hours from cannulation*

If parents/guardians with parental responsibility are available at patient admission to the Glenfield Hospital, an authorised member of the research team will approach them in order to explain the study and ask for emergency consent.

Parents/guardians with parental responsibility will be provided with an emergency parent/guardian/personal legal representative information leaflet at the time of their arrival at the Glenfield Hospital. At the same time, an authorised member of the research team will explain in summary the purpose of the study in person and will provide answers to any questions that might be raised. Due to the urgency of the situation, if parents/guardians are willing to take part in the study, they will be asked to provide a written emergency consent.

After parents/guardians' emergency consent, the samples will be collected following the protocol and the parents/guardians will be provided with a complete version of the parent/guardian/personal legal representative information leaflet. They should therefore have at least 12 hours to read and consider the information and to ask questions before being asked to decide whether they are willing to continue the study. An authorised member of the research team will approach again parents/guardians and will explain in details the research project, answer the questions and ask for full consent (59, 60).

In the event that a child withdraws, we will request that all patient's data and tissues collected until that time are retained for analysis. If this request is denied, all data will be removed and tissues disposed of. All the leaflets and forms will be approved by the local Research Ethics Committee (REC).

6.11.2 *Parents/guardians with parental responsibility not available within 12 hours from cannulation*

If parents/guardians with parental responsibility are not available at patient admission to the Glenfield Hospital, an authorised member of the research team will approach a personal legal representative (defined as in Table 4) in order to explain the study and ask for emergency consent.

As personal legal representative will be considered the following persons:

- Putative father
- Grandparents

The personal legal representative will be provided with an emergency parent/guardian/personal legal information leaflet at the time of his/her arrival at the Glenfield Hospital. At the same time, an authorised member of the research team will explain in summary the purpose of the study in person and will provide answers to any questions that might be raised. Due to the urgency of the situation, if the personal legal representative is willing to take part in the study, he/she will be asked to provide a written emergency consent.

After the personal legal representative's consent, the samples will be collected following the protocol and the personal legal representative will be provided with a complete version of the parent/guardian/personal legal representative information leaflet. He/she should therefore have at least 12 hours to read and consider the information and to ask questions before being asked to decide whether he/she is willing to continue the study. An authorised member of the research team will approach again the personal legal representative and will explain in details the research project, answer the questions and ask for full consent (59, 60).

In the event that a child withdraws, we will request that all patient's data and tissues collected until that time are retained for analysis. If this request is denied, all data will be removed and tissue disposed of. All the leaflets and forms will be approved by the local Research Ethics Committee (REC).

6.11.3 *Neither parents/guardians with parental responsibility nor personal legal representative available within 12 hours from cannulation*

If parents/guardians with parental responsibility and a personal legal representative are not available at patient admission to the Glenfield Hospital, an authorised member of the research team will approach a professional legal representative (defined as in Table 4) in order to explain the study and ask for emergency consent. The professional legal representative have to be a Consultant in Paediatric Intensive Care and/or ECMO not connected with the conduct of the trial. Before the start of the recruitment phase, the study will be explained to the whole medical staff working in the Paediatric Intensive Care Unit and in the ECMO team through several meetings. This will allow them to understand the details of the study in advance, consider all the information and ask questions.

The professional legal representative will be provided with an emergency professional legal representative information leaflet at the time of the child's arrival at the Glenfield Hospital. At the same time, an authorised member of the research team will explain in summary the purpose of the study in person and will provide answers to any questions that might be raised. Due to the urgency of the situation, if the professional legal representative is willing to take part in the study, he/she will be asked to provide a written emergency consent. After the professional legal representative's consent, the samples will be collected following the protocol.

As soon as possible, a member of the research team will approach parents/guardians with parental responsibility or a personal legal representative, explain in summary the project, and provide them with a complete version of the parent/guardian/personal legal representative information leaflet. They should therefore have at least 12 hours to read and consider the information and to ask questions before being asked to decide whether he/she is willing to continue the study. An authorised member of the research team will approach again the parents/guardians with parental responsibility or a personal legal representative and will explain in details the research project, answer the questions and ask for full consent (59-60).

In the event that a child withdraws, we will request that all patient's data and tissues collected until that time are retained for analysis. If this request is denied, all data will be removed and tissue disposed of. All the leaflets and forms will be approved by the local Research Ethics Committee (REC).

6.11.4 Satisfaction questionnaire

Perceptions of family members whose children participate in the study as to the appropriateness of the screening and consent process will be assessed by means of a 11 items questionnaire (Appendix 1) adapted from previous studies (61, 62). The questionnaire will be administered at the end of the study prior to hospital discharge.

6.12 Planned recruitment rate and duration of follow-up

On the basis of historical data we estimate that there will be a target population of 40-60 eligible patients over 12 months at Glenfield Hospital. We plan to recruit, 24 of all eligible patients. In a previous observational clinico-experimental study undertaken by this group [The p-MiVAKI study (63)], that also required serial blood sampling in children undergoing cardiac surgery, an 84.37% consent rate was achieved.

Participants will be followed up until discharge from UHL.

6.13 Likely rate of loss to follow-up, protocol violations and clinical data completeness

Until discharge from hospital, the likely losses to follow-up will be due to death or participant withdrawing, or more commonly incomplete collection of the samples. In a previous observational clinico-experimental study undertaken by this group [The p-MiVAKI study (63)], that also required serial blood sampling in children, clinical data showed a completeness of 84.09% as described in Table 5.

Table 5 – Data collection

Variable	Completeness (%)
Overall	84.09
Clinical variables	94.61
Clinical laboratory data	77.5
Categorical variables	100

Total sample collection reached a percentage of 93.75% (Table 6-7). Only in one case, parents refused consent for one sample donation because of children discomfort. All patients concluded the study and no major protocol violations were recorded.

Table 6 – Blood sample collection

	Patients (n)	Expected samples (n)	Collected samples (n)	Collected samples (%)
Patient's weight: 2-5 Kg	6	18	18	100%

Patient's weight: 5-20 Kg	14	42	41	95.2%
Patient's weight: > 20 Kg	4	12	9	75%
Total	24	72	68	94.4%

Table 7 – Urine sample collection

	Patients (n)	Expected samples (n)	Collected samples (n)	Collected samples (%)
Patient's weight: 2-5 Kg	6	18	18	100%
Patient's weight: 5-20 Kg	14	42	40	97.9%
Patient's weight: > 20 Kg	4	12	9	75%
Total	24	72	67	93.1 %

6.14 Expenses and benefits

Participants will not receive payment for taking part in the trial. As they will not be attending as outpatients above and beyond their normal care there will be no additional reimbursement for travel or other expenses.

7. Statistical Considerations

7.1 Sample Size

This is a feasibility study and no formal power calculation has been performed. Our sample size is based on our observations from the 24 patients in the p-MiVAKI study (63), where we have demonstrated significant differences in markers of platelet, leukocyte and endothelial activation between patients who subsequently did or did not develop AKI, and between those that did or did not receive transfusion.

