Study Objectives	
This is a pilot feasibility study that will establish the following:
 
 1. Recruitment rates and patient flows for 24 patients specified as the target population for the feasibility study 2. Withdrawal rate, and completeness of follow-up and data collection in a paediatric population at high risk for death and major morbidity 3. The proportions (categorical data) and variance (continuous data) for the primary and secondary outcomes of interest. These will be used to model the sample sizes and outcomes that may be used in a definitive study

	4. Perceptions of family members whose children participate in the study as to the appropriateness of the screening and consent process (Appendix 1)
Study Design	Prospective, single-centre observational feasibility study
Setting	The study will be carried out at a regional paediatric ECMO centre in the UK, the University Hospitals of Leicester NHS Trust
Planned Sample Size	24 children undergoing ECMO will be enrolled
Recruitment Rate	This unit performs over 60 neonatal and paediatric ECMO per year, of which at least 40 are expected to be caused by PPHN in infants
Subject Selection Criteria	
Participant may enter study if ALL of the following apply:
 
 1. Patients with a diagnosis of PPHN 2. Patients that require ECMO support as determined by the ECMO team 3. Patients aged less than 30 days 4. Emergency consent obtained within 12 hours from cannulation, and ultimately full consent 
Participant may not enter study if ANY of the following apply:
 
 1. PPHN is caused by a congenital heart pathology 2. ECMO is required for a congenital heart disease 3. Lack of consent
Primary outcome of interest	Markers of platelet, leukocyte and endothelial cell activation in arterial blood at baseline (12 hours after ECMO commencement) and then at 24, 48 and 72 hours post commencement and at weaning (end of ECMO support: 24 hours after decannulation) or immediately prior to ECMO support being stopped in case of death or treatment withdrawal

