Figure 1. Role of free haemoglobin in organ injury in REDWASH patients: N=60 patients receiving a mean of 3 units of blood randomised to standard care or red cell washing using the Fresenius CATS device. Results showed that red cell washing increased circulating free haemoglobin levels (A), which was due to the haemolysis during washing (B). Free haemoglobin led to a mild oxidative stress, as indicated by elevated carbonyl modifications in plasma proteins (C). Our *in vitro* experiments indicate that free haemoglobin and oxidative stress lead to endothelial activation, as indicated by higher levels of MV production (D). Higher levels of endothelial MV (estimated with flow cytometry) are also observed in patients transfused with washed blood (E) and correlate with carbonylation levels. Endothelial dysfunction most likely affected kidney function as indicated by NGAL levels (F) and higher incidence of AKI (G) identified according to the KDIGO criteria.

Washing of stored red cells also led to higher ATP content by increasing RBC metabolic rate when exposed to increased shear stress in extracorporeal circuits. This results in red cell activation manifested by MV shedding (fig. 2D) and accelerated ATP depletion. The released MV could further increase oxidative stress by directly delivering haem to endothelial cells (Camus et al., 2015) or causing vaso-occlusions in kidney (Camus et al., 2012). Given that virtually all neonatal ECMO patients are transfused with stored red cells, the parallels we have observed between adults and children undergoing cardiac surgery in terms of inflammatory responses, and the results of the REDWASH trial, we now suggest that activation of red cells by the centrifugal pump and shear stress within the ECMO circuit may contribute to increased serum hemoglobin levels and inflammatory red cell microparticles release. We hypothesise that levels of free hemoglobin and red cell derived microparticles will be associated with endothelial activation, increased markers of pulmonary leucocyte activation and platelet activation, acute kidney injury and potentially failure to wean from ECMO (43-53).

[figure not shown]

Figure 2. RBC biochemical properties and the role of RBC MV: ATP (A), 2,3-DPG (B) and osmotic fragility (C) levels in 20 days old RBC, before and after washing or rejuvenation. (D)RBC MV production in REDWASH patients.

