7.3 Plan of analysis

A statistical analysis plan will be drafted prior to analysis. Normally distributed data will be presented as means (standard deviation). Non normally distributed data will be presented as geometric means (95% confidence intervals). Dichotomous data will be presented as percentages. This data will be used to quantify the number of patients required to design a further prospective observational analysis.

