1.3 Sample Size

The Mi-ECMO study enrolled 24 patients. There was not a formal power calculation for this feasibility study. The sample size was based on the observations from a similar study, p-MiVAKI which had recruited 24 paediatric patients and was able to demonstrate differences in the primary outcomes, markers of platelets, leukocyte and endothelial activation, between those who did and did not develop AKI, and between those did and did not receive transfusion.

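### Half of the stated basis for 24 infants does not carry over to this population, and the SDs and proportions meant to size the next study are to be reported without intervals

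*Protocol*

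**What the plan says.** The Protocol synopsis sets the size: "24 children undergoing ECMO will be enrolled". Protocol 7.1 adds: "This is a feasibility study and no formal power calculation has been performed". SAP 1.3 agrees: "There was not a formal power calculation for this feasibility study". Both sections then give the same basis for the number. An earlier paediatric study, also of 24 patients, found differences in platelet, leukocyte and endothelial markers "between patients who subsequently did or did not develop AKI, and between those that did or did not receive transfusion". SAP 1.3 repeats the second contrast as "between those did and did not receive transfusion".

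Protocol 3.3, arguing for the hypothesis, begins a sentence with "Given that virtually all neonatal ECMO patients are transfused with stored red cells". It gives no percentage.

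The SAP treats transfusion as a volume, one of the covariates in the exploratory mixed models of SAP 4.4. The subgroups in SAP 4.5 are ECMO duration (within 7 days or longer) and AKI (with or without). Whether any red cells were given appears only in the SAP appendix, as a variable to report.

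Protocol section 4, objective 3, collects proportions and variances to model the sample size of a definitive study. Protocol 7.3 says: "This data will be used to quantify the number of patients required to design a further prospective observational analysis". For reporting, Protocol 7.3 specifies mean and SD, or geometric mean with a 95% confidence interval, and percentages. SAP 4.3 specifies mean and SD or median and quartiles, with numbers and percentages. Neither gives an interval for an SD or for a proportion.

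**The concern.** A reader of Protocol 7.1 or SAP 1.3 would take it that a cohort of 24 supports two contrasts, AKI and transfusion. By the Protocol's own account the second has almost no comparison group here.

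The job that the 24 infants are actually given is estimation for planning: supplying SDs and proportions for the next study. That calls for a statement of how precise those estimates will be, and there is none. An SD taken from 24 infants at face value can be well below the true SD, and required sample size moves with the square of the SD. The error therefore passes straight into the size of the definitive study.

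**Working it through.** **The plan's own figure.** The 24 cannot be reproduced. No significance level, power, effect or SD is stated; the number is taken over from the earlier study.

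**Transfusion contrast.** The Protocol gives no rate, so I assume a transfusion rate p of 90% to 99%. Expected untransfused infants = 24 × (1 − p); chance of none = p^24.

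| Assumed p | Expected untransfused | Chance of none |
|---|---|---|
| 90% | 2.4 | 8% |
| 95% | 1.2 | 29% |
| 98% | 0.5 | 62% |
| 99% | 0.2 | 79% |

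Detectable difference at 80% power, two-sided 5%, one value per infant, normal approximation: (1.960 + 0.842) × √(1/n1 + 1/n2).
- 22 v 2: 2.07 SD.
- 23 v 1: 2.86 SD.
- AKI contrast at the 64% quoted in Protocol 3.2 (0.64 × 24 = 15.4, so 15 v 9): 1.18 SD, or 1.24 SD by the noncentral t.

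The AKI split is far less lopsided, so that half of the rationale remains usable.

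**Precision of an SD from 24.** For roughly normal (or logged) data, 23 s²/σ² follows chi-square with 23 df. The 95% limits for σ are s × √(23/38.08) = 0.78 s and s × √(23/11.69) = 1.40 s. With 18 usable values they are 0.75 s and 1.50 s. This matters because SAP 4.7 imputes nothing beyond the quantification limits.

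**Effect on the next study.** Assume a two-group comparison of means, two-sided 5%, a known effect, and n computed from the observed s for a target power T. True power falls below 80% when s²/σ² < R, where R = [(1.960 + 0.842)/(1.960 + z_T)]². The probability is the chi-square (23 df) distribution function at 23 × R.

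| Target T | R | Chance of true power below 80% |
|---|---|---|
| 80% | 1.000 | 54% |
| 85% | 0.874 | 36% |
| 90% | 0.747 | 20% |
| 95% | 0.604 | 7% |

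Simulating 20,000 pilots at a 90% target, for true effects of 0.3 to 1.0 SD, gives 17% to 20% with the normal formula and 21% to 22% with the t-test. With 18 usable values the chance is 24% at a 90% target and 55% at an 80% target.

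**Planning on an upper limit.** The one-sided 80% upper limit for σ is s × √(23/17.19) = 1.157 s, which multiplies n by 1.157² = 1.34. The chance of missing the target, whatever it is, is then 20% by construction. For a 90% target, the chance of falling below 80% drops to about 4% (0.045).

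**Proportions.** Exact (Clopper-Pearson) 95% intervals, for illustration: 15/24 gives 41% to 81%; 0/24 gives 0% to 14%.

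**The case against.** The documents claim no power, and the quoted clause reports what the earlier study found; it is not a contrast planned here. Modelling transfusion volume suits a group in which nearly everyone is transfused. Deleting the clause changes no patient, analysis or result, and SAP 1.3 reports the 24 as already enrolled. All of this stands, and it makes the transfusion part a correction of rationale only.

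Several stronger readings are tempting and are not supported:
- That the transfusion contrast is impossible here. Protocol 3.3 leaves room for a few untransfused infants and gives no rate.
- That the next study will fall below 80% power one time in five. That is the 90%-target case only. The documents name no target power, significance level or effect, and the figure runs from 7% to 54% over plausible targets.
- That choosing 24 makes the next study more likely than not to be underpowered. A sample SD falls below the true SD slightly more than half the time at any pilot size: 53.9% at 24, 51.9% at 100, 51.3% at 200. Under a 90% target the median true power is still about 89%. What 24 affects is how far short the power may fall.
- That 24 is too few. Nothing in the documents shows this.

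The next study may also not be a comparison of means. The synopsis speaks of early biomarkers, which could be sized on diagnostic precision or event counts. The detectable differences above use one value per infant, whereas SAP 4.4 uses repeated measures. Where Protocol 7.3's interval for a geometric mean is reported, a log-scale SD can be recovered from it. These points limit the power figures. They do not remove the case for intervals on the quantities that the study exists to estimate.

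**Conclusion.** The point holds in a limited form. The transfusion half of the basis for 24 does not fit a population that the Protocol describes as almost wholly transfused; the AKI half does. Separately, the plan commits the pilot variances and proportions to sizing the next study without stating their precision or allowing for error in the SD.

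The 0.78 to 1.40 range for the SD assumes all 24 values of a roughly normal or logged marker; missing samples widen it. The power shortfalls also assume a two-group comparison of means, two-sided 5%, a known effect and a target that the documents do not give, so they should be quoted as a range with the target named. This is an inexpensive improvement to reporting and planning. It is no ground for recruiting more infants.

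**What to change.** - **Protocol 7.1 and SAP 1.3:** drop the transfusion contrast as a basis for 24, keep the AKI contrast, and state the precision that 24 gives: SD limits of 0.78 to 1.40 times the estimate, and an example interval for a proportion.
- **Protocol 7.3 and SAP 4.3:** report a 95% confidence interval for each SD, on the log scale for skewed markers and in addition to median and quartiles, with the number of values used. Report a 95% interval for each feasibility proportion, with its denominator.
- **When the data are used to size the next study:** show the required n at the observed SD and at an upper confidence limit of the SD, with the assumed effect and target power stated. The one-sided 80% limit (SD × 1.157, n × 1.34) is one reasonable convention; another may be chosen if it is named in advance.

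The cost is some wording and a little more analysis, with no extra patients here. The indicated size of the next study rises by about a third at that upper limit. The rationale edit is retrospective. SAP 4.1 places the analysis after the final dataset is ready, so the reporting changes can be made before it is run.
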